### Schema for CLL with Richter's transformation (Arm C)

 Total duration of treatment including both single-agent or combination therapy combined is a maximum of 24 months. NOTE: If patient is continuing to benefit from treatment after 12 months, they may continue to receive treatment up to a total duration of 24 months including both single-agent and combination therapy at investigator/sponsor discretion.

Q 3 months x 4

If CLL with Richter's transformation patients have achieved CMR (complete metabolic response) confirmed by bone marrow and PET/CT evaluation, patients could continue the treatment for 2 more cycles and stop the treatment at the discretion of the treating provider and enter observation.

Signal inhibitor can be continued or stopped at the end of therapy (12 or 24 months) per treating physician discretion.

 Disease measurements and lab parameters obtained after the last cycle of single-agent therapy are set as the baseline measurements/labs for the continuation phase.

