12. Research bone marrow aspirate specimens must be collected at the same time when clinical bone marrow tests are required (e.g. baseline, 6 and 12 months of therapy or other time when performed) and submitted. If bone marrow was performed prior to consenting the patient for this study, a repeat bone marrow is not required to obtain the research aspirate sample at baseline.
13. Adverse events, CBC, Cr and LFTs must be evaluated every cycle. For patients who tolerated therapy and have clinical benefits, they will be followed at each cycle for the first 6 months. Clinical response will be evaluated at 3 and 6 months. After 6 months of therapy, responsive or stable patients can be followed every other cycle by treating physician/provider until one or two years of total duration of therapy. However, patient will be followed by nurse at each cycle of treatment for adverse event assessment. They will be seen as needed by provider. Physical exam and tumor measurements are required only on cycles where the patient is evaluated by the treating physician. All patients who received at least 6 months of therapy and have shown clinical benefit will be evaluated again at 12 months for clinical response. For patients who continue therapy beyond 12 months, the above schedule is recommended. Further formal response evaluation is only required if there is clinical sign of disease progression. Other response evaluation is per discretion of treating physician.
14. For Follicular lymphoma grade 3 and CLL patients with Richter's transformation or Hodgkin transformation, PET/CT scan will be performed to replace CT at baseline, at 3, 6, and 12 months for response evaluation. Scans after baseline are not required for patients with lymphoplasmacytic lymphoma (Waldenstrom Macroglobulinemia) if utilizing IgM as the criteria for response. If patient had measurable nodes at baseline, then scans should be repeated.
15. For patients with lymphoplasmacytic lymphoma (Waldenstrom Macroglobulinemia) only when this is being used as the criteria for measurable disease.
16. Reticulocytes are required at baseline for all patients. After baseline may be ordered at physician discretion.
17. At 6 month visit. If there is no change from baseline, further testing is not required.

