## 16.0 Statistical Considerations and Methodology

16.1 Overview: This Phase II study will utilize a one-stage binomial design in each arm independently (Arms A, B, and C) to assess the overall response rate associated with single-agent MK-3475 in patients with relapsed and progressive CLL/SLL, including CLL patients with Richter's transformation (RS) or Hodgkin's transformation (Arm A and Arm C) and other types of relapsed and progressive low grade B cell NHL including FL, WM and marginal zone lymphoma (Arm B).

16.11 Endpoint: The primary endpoint of this trial is the proportion of patients who achieve a confirmed response to single-agent MK-3475. A confirmed response is defined to be a PR, nPR, CCR, CRi or CR (Arms A and B) or CMR, PMR, PR, or CR (Arm C) noted as the objective status at any time while on single-agent MK-3475. All patients meeting the eligibility criteria who have signed a consent form and have begun treatment will be evaluable for response, with the exception of patients determined to be a major violation.

16.12 Sample Size: This study is expected to require a maximum of 23 evaluable patients each in Arm A and Arm B. We anticipate accruing 1 additional patient in each arm to account for ineligibility, cancellation, major treatment violation, or other reasons. Therefore, this study is expected to accrue between 46 - 48 patients in these two arms.  
As of MCCC Addendum 3, due to promising response observed in CLL patients with Richter's transformation, an additional arm (Arm C) with 17 evaluable patients is added to the trial. We anticipate accruing 3 additional patients to account for ineligibility, cancellation, major treatment violation, or other reasons for a total of 20 patients on Arm C. These patients will be accrued to allow better evaluation of response and toxicity of single agent MK 3475 in patients with Richter's transformation. This study is now expected to accrue a maximum of 68 patients.

16.13 Accrual Rate and Study Duration: The anticipated accrual rate is approximately 2-4 patients per month. Therefore, the accrual period for this phase II study is expected to be approximately 2-3.0 years. The final analysis can begin as soon as the last patient has been observed for 6 months, or at approximately 3.0-3.5 years.  

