MCCC Addendum 3: In approximately 20 months, the study has accrued 41 patients. Based on current accrual rates, the total accrual period is now expected to be approximately 3.0 years. The final analysis can begin as soon as the last patient has been observed for 6 months, or approximately 3.5 years from trial opening.

16.2 Statistical Design:

16.21 Decision Rule for Arms A and B (to be evaluated in each arm independently): MK-3475 monotherapy induces an ORR of 39% in patients with ipilimumab-naïve melanoma by central independent RECIST review. The potential activity of this agent in relapsed CLL or low grade NHL has not been tested. Previous approved monoclonal antibodies, alemtuzumab or rituximab, have achieved ~20-30% ORR in CLL. We expect that CLL patients who develop resistance to novel CLL therapies will enroll into this clinical study. It is completely unknown how CLL patients will respond to any types of CLL therapy after they developed

Ibrutinib resistance. Therefore, it is logical to hypothesize that 30% ORR will be worthy of further testing in relapsed CLL and low grade NHL patients.

The largest success proportion where the proposed treatment strategy would be considered ineffective in this population is 10%. The smallest success proportion that would warrant subsequent studies with the proposed treatment strategy in this patient population is 30%. The following one-stage binomial design uses 23 evaluable patients to test the null hypothesis that the true success proportion in a given patient population is at most 10%.

16.211 Final Decision Rule: Enter 23 evaluable patients into the study. If 4 or fewer successes are observed in the first 23 evaluable patients, we will consider this regimen ineffective in this patient population. If 5 or more successes are observed in the first 23 evaluable patients, we may recommend further testing of this regimen in subsequent studies in this population.

16.212 Over Accrual: If more than the target number of patients are accrued, the additional patients will not be used to evaluate the stopping rule or used in any decision making process. Analyses involving over accrued patients are discussed in Section 16.34.

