16.3 Analysis Plan (to be evaluated in each arm independently)

16.31 Primary Outcome Analyses:

16.311 Definition: The primary endpoint of this trial is the proportion of patients who achieve a confirmed response to single-agent MK-3475. A confirmed response is defined to be a PR, nPR, CCR, CRi or CR (Arms A and B) or PMR, CMR, PR or CR (Arm C) noted as the objective status at any time while on single-agent MK-3475. All patients meeting the eligibility criteria who have signed a consent form and have begun treatment will be evaluable for response, with the exception of patients determined to be a major violation. For CLL patients with Richter's transformation, confirmed response is determined by response criteria defined for Richter's transformation.

16.312 Estimation: In each arm, the proportion of successes will be estimated by the number of successes divided by the total number of evaluable patients in that arm. Exact binomial confidence intervals for the true success proportion will be calculated. In addition, the confirmed response rate for all Richter's transformation patients (9 patients from Arm A and all patients in Arm C) will be calculated.

16.32 Secondary Outcome Analyses (to be evaluated in each arm independently; Arm C analyses may include the 9 Richter's transformation patients from Arm A): (For all outcomes associated with combination therapy in Arms A and C, disease measurements obtained after the last cycle of single-agent therapy are set as the baseline measurements for combination therapy).

16.321 Progression-free survival (PFS) for single-agent MK-3475 is defined as

the time from registration to the earliest date of documentation of disease progression while on single-agent MK-3475 or death due to any cause. In Arm A and Arm C, patients who initiate combination therapy for stable disease after 3 months of single-agent MK-3475 will be censored on the date that combination therapy is initiated.

In Arm A and Arm C, PFS for the combination of MK-3475 and the signal inhibitor is defined as the time from initiation of treatment with the combination therapy to the earliest date of documentation of disease progression while on combination therapy or death due to any cause.

The distribution of progression-free survival will be estimated using the method of Kaplan-Meier.

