We note that we will review grade 4 and 5 adverse events deemed “unrelated” or “unlikely to be related”, to verify their attribution and to monitor the emergence of a previously unrecognized treatment-related adverse event.

16.6 Results Reporting on ClinicalTrials.gov: At study activation, this study will have been registered within the “ClinicalTrials.gov” website. The Primary and Secondary Endpoints along with other required information for this study will be reported on ClinicalTrials.gov. For purposes of timing of the Results Reporting, the initial estimated completion date for the Primary Endpoint of this study is 3.5 years after the study opens to accrual. The definition of “Primary Endpoint Completion Date” (PECD) for this study is at the time all patients registered have achieved a response or have discontinued treatment before achieving a response.

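### Section 16.13 lets the final analysis start at last patient plus 6 months, before the primary endpoint need be fully ascertained; one trigger should serve 16.13 and 16.6 (minor)

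*Combined protocol and SAP*

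**What the plan says.** - **Timing of the analysis (16.13, text for Addendum 3).** "The final analysis can begin as soon as the last patient has been observed for 6 months, or approximately 3.5 years from trial opening". The same paragraph reports 41 patients in about 20 months and expects accrual to last about 3.0 years.
- **Endpoint (16.11 and 16.311).** A success is a qualifying response "noted as the objective status at any time while on single-agent MK-3475". There is no 6-month limit.
- **Evaluations.** Sections 11.0 and 11.6 schedule formal response evaluation at 3, 6 and 12 months. Footnote 13 of the 4.1 test schedule says that patients treated for at least 6 months who have shown benefit "will be evaluated again at 12 months for clinical response". Beyond 12 months: "Further formal response evaluation is only required if there is clinical sign of disease progression".
- **Treatment length.** Section 13.3 plans 12 months. The Arm C schema adds that patients who are still benefiting "they may continue to receive treatment up to a total duration of 24 months".
- **Completion of the primary endpoint (16.6).** It is reached "at the time all patients registered have achieved a response or have discontinued treatment before achieving a response", yet "the initial estimated completion date for the Primary Endpoint of this study is 3.5 years after the study opens to accrual".
- **Counting (16.312).** The rule, applied arm by arm, is that "the proportion of successes will be estimated by the number of successes divided by the total number of evaluable patients in that arm". Section 16.3 names no data cut and gives no rule for a patient who is on single agent without a response when the data are cut.
- **Arm C decision (16.231).** Five or more successes in the first 17 evaluable patients may lead to further testing. Four or fewer means that the regimen is considered ineffective.

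**The concern.** The endpoint window is open-ended and its last scheduled formal evaluation is at month 12, but the analysis may start when the last patient has been observed for 6 months. Under 16.312 every evaluable patient is in the denominator. A patient on single agent with the month-12 evaluation still to come would therefore enter the decision as a non-success. Section 16.6 holds the endpoint open until such a patient responds or stops, yet gives a date that matches the shorter rule.

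What is at stake is mainly Arm C. Arms A and B closed to accrual in April 2016 and April 2017, so if Arm C enrols last, its late entrants are the ones with short follow-up. An early cut can only lower the Arm C success count. Because the trial is open-label and decided on a single count, it is also better that the cut date is not left to choice.

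**Working it through.** **1. The plan's own figures.** Accrual of 3.0 years plus 0.5 years of observation gives 3.5 years, so 16.13 reproduces. For Arm C, the probability of 5 or more successes in 17 is 0.874 at a true rate of 0.40 (stated 0.87) and 0.0987 at 0.15 (stated 0.10). Both reproduce.

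**2. Dates under other triggers.** The observed rate is 41/20 = 2.05 patients per month, so the 68th patient enters at 68/2.05 = 33.2 months.

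| Trigger | Accrual ends at 36 months | Accrual ends at 33.2 months |
|---|---|---|
| Last patient + 6 months | 42 months = 3.5 years | 39.2 months = 3.3 years |
| Last patient + 12 months | 48 months = 4.0 years | 45.2 months = 3.8 years |
| Last patient + 24 months (16.6 read literally, maximum treatment) | 60 months = 5.0 years | 57.2 months = 4.8 years |

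With accrual to 36 months, the 16.6 definition is met at 3.5 years only if every late entrant has by then responded or stopped.

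**3. How many of the first 17 Arm C patients could be exposed.** Assume that Arm C enters evenly from month 20 (not stated in the plan). Patient *i* of *n* then has follow-up of (cut − 20) − (entry period × *i*/*n*). Count those with under 12 months, taking *n* = 20 if all accrued patients are evaluable and *n* = 17 if only 17 are.

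| Scenario | n = 20 | n = 17 |
|---|---|---|
| Entry over 16 months, cut at month 42 | 22 − 16i/20: 5 (i = 13-17) | 22 − 16i/17: 7 (i = 11-17) |
| Entry over 13.17 months, cut at month 42 | 22 − 13.17i/20: 2 (i = 16-17) | 22 − 13.17i/17: 5 (i = 13-17) |
| Entry over 13.17 months, cut at month 39.2 | 19.17 − 13.17i/20: 7 (i = 11-17) | 19.17 − 13.17i/17: 8 (i = 10-17) |
| Slower entry over 24 months (assumed), cut at last patient + 6 | 30 − 24i/20: 2 (i = 16-17) | 30 − 24i/17: 5 (i = 13-17) |

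These are upper limits. A patient who has already responded or left single agent is not affected by the cut.

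**4. Effect on the decision.** Let *m* be the number of exposed patients and *f* the share of their responses that arise after the cut. The documents give no value for *f*; 5-30% is assumed. Then X = Bin(17 − m, p) + Bin(m, p(1 − f)), with success if X ≥ 5. At p = 0.40:

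| m | f = 5% | 10% | 20% | 30% |
|---|---|---|---|---|
| 0 | 0.874 | 0.874 | 0.874 | 0.874 |
| 2 | 0.870 | 0.866 | 0.857 | 0.849 |
| 5 | 0.864 | 0.853 | 0.829 | 0.804 |
| 7 | 0.859 | 0.843 | 0.808 | 0.769 |
| 8 | 0.857 | 0.839 | 0.797 | 0.750 |

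At p = 0.15 the chance of a positive result falls from 0.099 to 0.094-0.071 for m = 5 and to 0.092-0.062 for m = 7. The change is always downward.

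**5. A side point on month 6.** Section 11.0 puts the month-6 evaluation at about day 189, and 6.5 allows treatment to start up to 14 days after registration. Section 16.13 does not say where observation starts. If it starts at registration, the last patient's month-6 evaluation could fall at 14 + 189 = day 203, after a cut at day 183.

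**The case against.** The wording of 16.13 is permissive: it sets an earliest start and forbids nothing later. Section 16.6 is written for results reporting and calls its date an initial estimate. Both sections can therefore be satisfied at once. This stands, and it rules out reading the two as a direct contradiction. What remains is that neither fixes the data cut for the decision rule, and that the 16.6 definition and its date agree only in a favourable case.

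The exposed group may also be nearly empty. Under 7.3 and 13.1, progression at any time or stable disease at month 3 permits adding a signal inhibitor, which ends the single-agent window. Section 11.1, written for the CLL criteria, envisages single agent after month 3 mainly for patients with neither progression nor stable disease. Footnote 13 limits its month-12 evaluation to patients with benefit. This is a strong reason to expect a small effect. It does not remove the point: adding the inhibitor is optional, and footnote 13 and 7.2 both provide for stable patients continuing after 6 months.

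Finally, the late-response share is assumed. In the 16-month, 20-evaluable scenario the five exposed patients already have 8.4-11.6 months of follow-up, so for them *f* is essentially the share of responses first seen at month 12. This also stands, and the lower power figures are limits, not expectations.

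**Conclusion.** The point holds as a minor one. Section 16.13 permits a final analysis before the primary endpoint need be fully ascertained, and 16.6 attaches the same 3.5 years to a more demanding definition. The likely cost is slight: power of 0.85-0.87 against 0.874 if 2 of 17 patients are affected and 5-30% of their responses come late. A fall to 0.75-0.80 needs 5-8 affected patients and 30% late responses, and is an upper limit. All of these figures rest on the assumed entry pattern and late-response share.

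A reader might infer more than the documents support:
- **That the error rates are wrong or that type I error is inflated.** The tabulated values reproduce, and an early cut can only reduce the chance of a positive result.
- **That two further months must be added for confirmation of response.** The 2-month duration belongs to the CLL criteria in 11.21 and 11.22. Section 16.311 applies the Richter's criteria to Richter's patients, so that delay does not arise in Arm C.
- **That responses first seen after month 12 should be barred from the decision.** This would narrow the endpoint in 16.11 and 16.311, which counts a response at any time on single agent.

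**What to change.** State one trigger in both 16.13 and 16.6: the primary analysis is done when every evaluable patient has responded, has left single-agent MK-3475, or has completed the month-12 evaluation. Restate the date in both sections as up to about 4.0 years from opening, or about 3.8 years at the observed accrual rate. Leave the endpoint definition unchanged, and add one sentence that any response first seen after the cut is reported as an update.

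The trigger also avoids the wait of up to 5.0 years that 16.6 allows when read literally, during which formal evaluation after month 12 is required only for signs of progression. The cost is a wording change, with no extra visits or patients. The read-out is up to about 6 months later, and only if a patient is still pending at the 6-month mark.

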16.3 Analysis Plan (to be evaluated in each arm independently)

16.31 Primary Outcome Analyses:

16.311 Definition: The primary endpoint of this trial is the proportion of patients who achieve a confirmed response to single-agent MK-3475. A confirmed response is defined to be a PR, nPR, CCR, CRi or CR (Arms A and B) or PMR, CMR, PR or CR (Arm C) noted as the objective status at any time while on single-agent MK-3475. All patients meeting the eligibility criteria who have signed a consent form and have begun treatment will be evaluable for response, with the exception of patients determined to be a major violation. For CLL patients with Richter's transformation, confirmed response is determined by response criteria defined for Richter's transformation.

16.312 Estimation: In each arm, the proportion of successes will be estimated by the number of successes divided by the total number of evaluable patients in that arm. Exact binomial confidence intervals for the true success proportion will be calculated. In addition, the confirmed response rate for all Richter's transformation patients (9 patients from Arm A and all patients in Arm C) will be calculated.

16.32 Secondary Outcome Analyses (to be evaluated in each arm independently; Arm C analyses may include the 9 Richter's transformation patients from Arm A): (For all outcomes associated with combination therapy in Arms A and C, disease measurements obtained after the last cycle of single-agent therapy are set as the baseline measurements for combination therapy).

16.321 Progression-free survival (PFS) for single-agent MK-3475 is defined as

the time from registration to the earliest date of documentation of disease progression while on single-agent MK-3475 or death due to any cause. In Arm A and Arm C, patients who initiate combination therapy for stable disease after 3 months of single-agent MK-3475 will be censored on the date that combination therapy is initiated.

In Arm A and Arm C, PFS for the combination of MK-3475 and the signal inhibitor is defined as the time from initiation of treatment with the combination therapy to the earliest date of documentation of disease progression while on combination therapy or death due to any cause.

The distribution of progression-free survival will be estimated using the method of Kaplan-Meier.

16.322 Treatment-free survival (TFS) for single-agent MK-3475 is defined as the time from registration to the date of initiation of subsequent treatment for CLL/SLL or lymphoma or death due to any cause. In Arm A and Arm C, the initiation of combination therapy with MK-3475 and the signal inhibitor will be considered subsequent treatment.

In Arm A and Arm C, TFS for the combination of MK-3475 and the signal inhibitor is defined as the time from initiation of combination therapy to the date of initiation of subsequent treatment for CLL/SLL or death due to any cause.

The distribution of treatment-free survival will be estimated using the method of Kaplan-Meier.

16.323 The time to next treatment (TNT) for single-agent MK-3475 is defined as the time from registration to the date of initiation of subsequent treatment for CLL/SLL or lymphoma. In Arm A and Arm C, the initiation of combination therapy with MK-3475 and the signal inhibitor will be considered subsequent treatment.

In Arm A and Arm C, TNT for the combination of MK-3475 and the signal inhibitor is defined as the time from initiation of combination therapy to the date of initiation of subsequent treatment for CLL/SLL.

The distribution of time to next treatment will be estimated using the method of Kaplan-Meier.

16.324 The complete response rate will be estimated by the number of patients who achieve a CRI or CR (Arms A and B) or CMR or CR (Arm C) divided by the total number of evaluable patients. Complete response rate will be evaluated for single-agent MK-3475 in each arm and also for the combination of MK-3475 and the signal inhibitor in Arm A and C. All evaluable patients will be used for this analysis. Exact binomial 95% confidence intervals for the true complete response rate will be calculated in each arm.

16.325 Duration of response (DR) is defined for all evaluable patients who have achieved a PR, nPR, CCR, CRI, or CR (Arms A and B) or PMR, CMR, PR or CR (Arm C) as the date at which the patient's objective status is first noted to be a PR, nPR, CCR, CRI, or CR (Arms A and B) or PMR, CMR, PR or CR (Arm C) to the earliest date relapse is documented. Duration of response will be evaluated for single-agent MK-3475 in each

arm and also for the combination of MK-3475 and the signal inhibitor in Arm A and C. The distribution of duration of response will be estimated using the method of Kaplan-Meier.

16.326 Overall survival is defined as the time from registration to death due to any cause. The distribution of overall survival will be estimated using the method of Kaplan-Meier.

16.327 Arm A and Arm C: The overall response rate for the combination of MK-3475 and the signal inhibitor (targeted agents) will be estimated by the number of patients with an objective status of CR, CRi, nPR, CCR or PR (Arm A) or PMR, CMR, PR or CR (Arm C) while on the combination therapy divided by the total number of evaluable patients. All evaluable patients who receive the combination therapy will be used for this analysis. Exact binomial 95% confidence intervals for the true overall response rate to the combination will be calculated. In addition, the responders on this study will be further examined in an exploratory manner to determine if there are any patterns in prognostic factors or disease characteristics, including whether the patient had a Richter's transformation or Ibrutinib-resistant disease, for both single-agent MK-3475 and combination therapy responders.

16.328 Adverse Events: All eligible patients that have initiated treatment will be considered evaluable for assessing adverse event rate(s). The maximum grade for each type of adverse event will be recorded for each patient, and frequency tables will be reviewed to determine patterns. Additionally, the relationship of the adverse event(s) to the study treatment will be taken into consideration. Adverse events will be evaluated for single-agent MK-3475 in each arm and also for the combination of MK-3475 and the signal inhibitor in Arm A and Arm C.

16.33 Correlative Analyses:

16.331 PD-1, PD-L1 and PD-L2 will be measured for each patient at baseline and during treatment. Each measure will be summarized descriptively by median, min, max and interquartile range. Overall response and complete response will be correlated with each measure using Wilcoxon rank sum test. The relationship between each measure and time to event measures (DR, TNT, PFS) will be evaluated using Cox proportional hazard models.

16.332 Markers of immune modulation and immune profiles will be summarized descriptively by median, min, max, and interquartile range (continuous factors) or frequency distribution (categorical factors) at each time point. Patterns over time will be summarized by absolute difference or relative change. Changes across time will be assessed using paired analyses, including Wilcoxon signed rank tests for continuous measures and McNemar's tests for categorical measures. Overall response and complete response will be correlated with continuous factors using Wilcoxon rank sum tests. Jitplots will be used to visually examine differences between groups for continuous factors. Overall response and complete response will be correlated with categorical factors using Fisher's exact tests.

16.34 Over Accrual: If more than the target number of patients are accrued, the additional patients will not be used to evaluate the stopping rule or used in any decision making processes; however, they will be included in final endpoint estimates and confidence intervals.

16.4 Safety Analysis Phase (Arm A and B only):

A safety analysis will be performed after the first 12 patients (6 each arm for Arm A and B) have been accrued to the study. Accrual will be temporarily halted while these patients are followed for one cycle to assess adverse events. If 2 or more of the first 6 patients in either arm experience a DLT as defined below, then accrual will continue to be temporarily suspended to the arm affected. All toxicity data will be reviewed by the study team and a decision will be made about whether the starting dose needs to be adjusted or the protocol should be continued.

Toxicity will be measured per NCI-CTCAE version 4. DLT is defined as an adverse event possibly, probably, or definitely related to study treatment that meets one of the following:

- hepatic toxicity defined as AST or ALT  $> 5 - 10 \times$  ULN for  $> 4$  weeks; Total bilirubin  $> 5 \times$  ULN for  $> 4$  weeks ; Concurrent AST or ALT  $> 3 \times$  ULN and total bilirubin  $> 2 \times$  ULN (excluding liver involvement by CLL or lymphoma) for  $> 4$  weeks (potential Hy's Law case)
- grade 4 non-hematological toxicity[except weight loss or fatigue or laboratory abnormalities not associated with clinical sequelae] lasting longer than 4 weeks despite of holding therapy and supportive treatments
- Any grade 5 AE

16.5 Data & Safety Monitoring:

16.51 The principle investigator(s) and the study statistician will review the study at least twice a year to identify accrual, adverse event, and any endpoint problems that might be developing. The Mayo Clinic Cancer Center (MCCC) Data Safety Monitoring Board (DSMB) is responsible for reviewing accrual and safety data for this trial at least twice a year, based on reports provided by the MCCC Statistical Office.

16.52 Adverse Event Stopping Rules (to be evaluated in each arm independently for single-agent MK-3475 and separately for combination therapy): The stopping rules specified below are based on the knowledge available at study development. We note that the Adverse Event Stopping Rule may be adjusted in the event of either (1) the study re-opening to accrual or (2) at any time during the conduct of the trial and in consideration of newly acquired information regarding the adverse event profile of the treatment(s) under investigation. The study team may choose to suspend accrual because of unexpected adverse event profiles that have not crossed the specified rule below.

Single-agent MK-3475: Accrual will be temporarily suspended to the affected arm if at any time we observe events considered at least possibly related to study treatment during cycles with single-agent MK-3475 (i.e. an adverse event with attribute specified as "possible," "probable," or "definite") that satisfy one of the following:

- If 4 out of the first 12 treated patients experience a DLT as defined in Section 16.4

- If after the first 12 patients have been treated, 30% of all patients experience a DLT as defined in Section 16.4.

Combination of MK-3475 and signal inhibitor (Ibrutinib or Idelalisib) in Arm A and Arm C: Initiation of treatment with the combination (addition of Ibrutinib or Idelalisib) will be halted in Arm A and Arm C if at any time we observe events considered at least possibly related to study treatment during cycles with the combination (i.e. an adverse event with attribute specified as “possible,” “probable,” or “definite”) that satisfy one of the following:

- If 2 out of the first 6 treated patients experience a DLT as defined in Section 16.4
- If after the first 6 patients have been treated, 30% of all patients experience a DLT as defined in Section 16.4.

We note that we will review grade 4 and 5 adverse events deemed “unrelated” or “unlikely to be related”, to verify their attribution and to monitor the emergence of a previously unrecognized treatment-related adverse event.

16.6 Results Reporting on ClinicalTrials.gov: At study activation, this study will have been registered within the “ClinicalTrials.gov” website. The Primary and Secondary Endpoints along with other required information for this study will be reported on ClinicalTrials.gov. For purposes of timing of the Results Reporting, the initial estimated completion date for the Primary Endpoint of this study is 3.5 years after the study opens to accrual. The definition of “Primary Endpoint Completion Date” (PECD) for this study is at the time all patients registered have achieved a response or have discontinued treatment before achieving a response.

